8.3.2 Weeks 52 and 104 – All Participants

The Data Collection Visits at Weeks 52 (\pm 3 months*) and 104 (\pm 14 days) will take place at the study site for all participants in both study groups. Weight, waist circumference, blood pressure and pulse rate will be recorded in line with study SOPs, any AEs/SAEs will be noted, and documentation of inclusion/exclusion criteria and changes in medication and/or diseases will be performed. Blood samples for standard laboratory testing of biochemical outcomes (HbA1c, FBC, U+Es, lipids, LFTs, TFTs, amylase) will be taken and participants will be requested to complete research questionnaires (see Appendix 3). A pregnancy test will take place for all female participants of child-bearing potential (in both standard care and LIRA 3mg targeted prescribing pathway groups).

A urine ACR will be performed for participants with diabetes, prediabetes and hypertension. All participants will complete the Epworth Sleepiness Scale to capture any improvement/decline in daytime sleepiness during the course of the study and the Stop Bang questionnaire to capture any undetected OSA cases, at 3 data collection visits (Baseline, Weeks 52 and 104). OSA patients will be managed through their local sleep clinic as per standard care. Those participants that are patients of the sleep clinic will have their notes reviewed to determine whether or not they are CPAP compliant and thus ‘successful’ against the below criteria.

- a. CPAP usage \geq 4 hrs/night = successful
- b. CPAP usage $<$ 4 hrs/night = struggling
- c. CPAP usage \leq 1 hrs/night = failure

Additional procedures at **Weeks 52 and 104** for the participants in the standard care group who have been prescribed and started anti-obesity medications (for example Orlistat) will be to ascertain whether they are still on the medication, their adherence, and any side effects.

Additional procedures at the **Week 52** visit for all participants who are on **LIRA 3mg** will include:

- Identification of participants on LIRA 3mg who have lost $\geq 15\%$ weight loss and meet the pre-specified criteria to continue on LIRA 3mg. These participants will meet the study clinician in order to be offered LIRA 3mg for another 52 weeks, to receive a new prescription of LIRA 3mg and to discuss adherence with the treatment and any side effects. Pregnancy testing will be undertaken as standard for this visit and clear instructions regarding contraception until the end of the study will be provided
- Participants on LIRA 3mg who did not reach the target of $\geq 15\%$ weight loss will meet the study clinician who will explain to them that they cannot continue on the medication any longer and that they will instead continue in the study on the Tier 3 programme with standard care. These participants will remain in the intervention group (targeted prescribing pathway), but will not receive LIRA 3mg as per the pre-specified stopping rules.

The purpose of the long-term (52-104 weeks) follow-up is to examine whether LIRA 3mg will help the “early and good” responders to maintain weight loss $\geq 15\%$ in comparison with the control group over a longer period of time. Additional procedures at the **Week 104** visit for all participants will include:

- The study clinician at each site will assess all the patients who participated in the study that have not been referred for bariatric surgery
- Participants who had significant weight regain during the second year in either treatment group will be discussed in Tier 3 MDT and may include a recommendation to their GP to refer them to Tier 4 service for bariatric surgery
- For participants who are on LIRA 3mg: the clinician will make a recommendation to the participant’s GP as to whether or not they should continue on the medication long-term, pending the local prescribing guidelines. Please note: participants on LIRA 3mg targeted prescribing pathway will only receive study medication for a maximum of 106 weeks (4 weeks titration, 100 weeks at 3mg, +/- 2 weeks visit window). For those participants that achieve more than 15% weight loss or a BMI $< 35\text{kg/m}^2$ prior to the 104 weeks, treatment with LIRA 3mg will be continued unless the patient begins to experience side-effects.

In an attempt to aid retention for the primary end point (week 52 – V11) all participants will be offered an incentive payment of £25 that will be paid on completion of the week 52 (visit 11) and dependant on us having weight data for that visit.

In response to the COVID19 global pandemic an interim time point for the quality of life questionnaires has been added (HSRUQ, TSQM, EQ-5D, IWQOL-Lite, IPAQ-Long and PHQ-9). These will be sent out to all participants during the COVID19 pandemic.

*Where possible the week 52 visit should continue to be scheduled within the (± 14 days) study visit window, however to aid retention and to help maximise data collection for the study primary end point, the week 52 visit window can be extended to ± 3 months.

8.4 Clinical Review (safety and retention) Visits (Weeks 2, 4, 8, 12, 16, 20, 32, 40 and 78) – All Participants

The Clinical Review visits will take place with a member of the research team at the study site. Where appropriate, the Clinical Review visits will be arranged in conjunction with the standard Tier 3 service appointments that participants will be scheduled to attend (e.g. appointments with the dietitian). Additional study visits will be arranged in the event where this might not be possible. The participant appointment schedule will depend on the Tier 3 service schedule, the date of the required Clinical Review Visit, and the availability of participants. The participant's adherence to the Tier 3 programme will also be reviewed. The research team will endeavour to maintain a low level of burden for these multiple visits. For participants in both arms of the study visits held at 2/52 (visit 3), 4/52 (visit 4), 12/52 (visit 6), 20/52 (visit 8), 40/52 (visit 10) and 78/52 (visit 12 for LIRA arm/13 for control arm) will be defined as 'optional' to reduce study burden and maximise participant retention, as per the visit schedule. Our experience in undertaking successful longitudinal research with multiple follow-ups will support these follow-up visits. The frequency of appointments for the Tier 3 service offered to the participants in both groups will continue as per the standard practice for each Tier 3 service.

During these Clinical Review Visits, participant eligibility will be re-checked and consent for continuation in the study will be re-confirmed. Weight, waist circumference, blood pressure and pulse rate will be recorded in line with study SOPs, any AEs/SAEs will be noted, and documentation of inclusion/exclusion criteria and changes in medication and/or diseases will be performed.

For patients on LIRA 3mg, monitoring of any problems and side effects, adherence with the injection, and advice on dose titration (at Weeks 2 and 4) as per the pre-specified protocol will take place during these visits. A pregnancy test will take place for all female participants of child-bearing potential who are in the targeted prescribing pathway and continue to be eligible to receive supply of LIRA 3mg. Clear instructions regarding contraception until the end of the study will be given at each visit.

Additional procedures at the **Week 16** visit for all participants who are on **LIRA 3mg** will include:

- Identification of participants on LIRA 3mg who have lost $\geq 5\%$ weight loss and meet the pre-specified criteria to continue on LIRA 3mg. These participants will meet the study clinician in order to be offered LIRA 3mg for another 16 weeks, to receive a new prescription of LIRA 3mg and to discuss adherence with the treatment and any side effects. Pregnancy testing will be undertaken as standard for this visit and clear instructions regarding contraception until the end of the study will be provided.
- Participants on LIRA 3mg who did not reach the target of $\geq 5\%$ weight loss will meet the study clinician who will explain to them that they cannot continue on the medication any longer and that they will instead continue in the study on the Tier 3 programme with standard care. These participants will remain in the intervention group (targeted prescribing pathway), but will not receive LIRA 3mg as per the pre-specified stopping rules.

Additional procedures at the **Week 32** visit for all participants will include:

- Blood samples for standard laboratory testing of biochemical outcomes (HbA1c, FBC, U+Es, lipids, LFTs, TFTs, amylase) will be taken for all participants
- A urine ACR will be performed for participants with diabetes, prediabetes and hypertension for all participants
- Participants in the standard care group who have been prescribed and started on anti-obesity medications (for example Orlistat) will be monitored to ascertain whether they are still on the medication, their adherence, and any side effects
- Participants on LIRA 3mg who have lost $\geq 10\%$ weight loss and meet the pre-specified criteria to continue on LIRA 3mg. These participants will meet the study clinician in order to be offered LIRA 3mg for another 24 weeks, to receive a new prescription of LIRA 3mg and to discuss adherence with the treatment and any side effects. Pregnancy testing will be undertaken as standard for this visit and clear instructions regarding contraception until the end of the study will be provided
- Participants on LIRA 3mg who did not reach the target of $\geq 10\%$ weight loss will meet the study clinician who will explain to them that they cannot continue on the medication any longer and that they will instead continue in the study on the Tier 3 programme with standard care. These participants will remain in the intervention group (targeted prescribing pathway) for the purpose of analysis, but will not receive LIRA 3mg as per the pre-specified stopping rules.

8.4.1 Additional Clinical Review (safety and retention) Visits for LIRA 3mg group (Weeks 65 and 91)

These two additional Clinical Review visits will take place with a member of the research team at the study site for only those participants in the intervention group who are still on treatment with LIRA 3mg. The agenda for these visits will be identical to the other nine Clinical Review Visits as described above in Section 8.4. The purpose of these visits is to provide participants with a new prescription of LIRA 3mg and to discuss adherence with the treatment and any side effects.

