6.2 Intervention (Targeted Prescribing Pathway)

The NHS Weight Management pathway is divided into four distinct tiers:

Tier 1: health promotion

Tier 2: lifestyle interventions

Tier 3: specialist multidisciplinary weight management services

Tier 4: bariatric surgery

Across the UK, each region has a specialist Tier 3 obesity and/or weight management service or equivalent, usually referred to as Tier 3. This includes a clinician led multidisciplinary team approach, potentially including a specialist physician, nurse, dietitian, psychologist, physiotherapist, etc. From this point forwards, Tier 3 specialist weight management and/or equivalent services will be referred to as 'Tier 3' throughout the remainder of this protocol.

Participants in the intervention group will receive the same standard care as those in the control group, i.e. the best medical practice delivered by the Tier 3 service at each site. Additionally, at baseline, LIRA 3mg will be prescribed to all of the participants in the intervention group at a starting dose of 0.6mg daily. Dose escalation of Liraglutide will occur according to a pre-specified titration protocol, from 0.6mg to a maximum of 3.0mg daily. Liraglutide dose will be initiated at 0.6mg and then increased to 1.2mg in Week 2, 1.8mg in Week 3, 2.4mg in Week 4, and 3.0mg in Week 5. Participants in the intervention group will be aware that the LIRA 3mg treatment may be stopped at various time points throughout the duration of the study and that continued use of LIRA 3mg is based upon their response to the treatment in terms of them achieving pre-defined weight loss targets at 16, 32 and 52 weeks.. Specifically, participants in the intervention group will continue to be prescribed LIRA 3mg for the 104 week duration of the study, unless one of the following stopping rules applies:

1st stopping rule:

After 16 weeks (\pm 14 days) on the medication, only those participants who have lost $\geq 5\%$ of their baseline weight will be offered further treatment with LIRA 3mg for another 16 weeks. Participants who have not met this weight loss target will have their LIRA 3mg treatment stopped but will still continue in the targeted prescribing pathway but will receive standard care only during the remainder of the study.

2nd stopping rule:

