7.2 Inclusion Criteria

To be considered eligible to participate in this study, a patient must:

- be aged between 18-75 years old (inclusive)
- understand written and spoken English
- be able to give informed consent
- have a BMI ≥ 35 kg/m 2
- have been referred to the Tier 3 service in one of the participating sites
- have a stable body weight (less than 5kg self-reported change during the previous 12 weeks)
- have at least one of prediabetes, diabetes, hypertension, and/or obstructive sleep apnoea, as defined below:
 - prediabetes (defined as established diagnosis of impaired fasting glycaemia (IFG) from GP and/or established diagnosis of impaired glucose tolerance (IGT) from GP and/or HbA1C 42-47 mmol/mol (6-6.4%) without glucose lowering medications, at a blood test during the last 6 months)
 - diabetes (defined as established diagnosis of Type 2 diabetes from GP and/or HbA1C ≥ 48 mmol/mol ($\geq 6.5\%$) at a blood test during the last 6 months] and/or being treated with any combination of lifestyle, metformin, sulphonylureas, Thiazolidinediones (TZDs) or SGLT-2)
 - hypertension treated (defined as being on antihypertensive treatment with or without a diagnosis of hypertension from GP) or untreated (defined as Systolic Blood Pressure ≥ 140 mmHg at two consecutive visits at the Tier 3 clinic),
 - obstructive sleep apnoea (on CPAP or established diagnosis of Apnoea Hypopnoea Index ≥ 15 at sleep studies during the last 12 months).

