8.8.4 Handling of participants after permanent treatment discontinuation

This study observes the effect of a targeted prescribing pathway (i.e. the use of LIRA 3mg when stopping rules are applied in combination with standard care in a Tier 3 service for patients with severe and complex obesity) compared with standard care alone. In case the GP or PI stops treatment or a participant withdraws from treatment with LIRA 3mg, e.g. for safety reasons, the participant will be offered standard care and the observation will continue.

If LIRA 3mg is stopped for other reasons not related to the applied stopping rules, it should be determined whether the stop can be made temporarily; permanent discontinuation of LIRA 3mg should be a last resort. Any discontinuation of the drug for reasons not related to the stopping rules should be fully documented in the CRF and medical records.

Participants must be instructed to notify the Investigator immediately if they become pregnant during the trial. Pregnancy will result in permanent treatment discontinuation (this will apply to both the LIRA 3mg and the standard care groups). The Investigator must report any pregnancy during the study to Novo Nordisk except for pregnancies occurring in the screening period prior to study treatment. Participants will give consent on enrolment that the Investigator will report any pregnancy during the study to Novo Nordisk and they will be asked to provide information about the pregnancy, delivery and the health of her infant until one month of age. Any AE in the child will be reported.

Participants will be followed according to the study procedures as specified in this protocol up to the scheduled date of study completion. If possible, and after the permanent discontinuation of investigational drug, the participants will be assessed using the procedure normally planned for the last onsite visit, if appropriate. All cases of permanent treatment discontinuation should be recorded by a member of the research team in the appropriate pages of the CRF and medical records when considered as confirmed. Study Sponsor is to be informed.

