3.3.3 Per Protocol Population

The per protocol population is defined as all participants who were compliant with their randomised treatment group, analysed according to the treatment group to which they have randomised at baseline. Participants in the standard care group are defined as treatment compliant if they complete at least 70% of the planned contacts in the Tier 3 service. Participants in the intervention group are defined as treatment compliant if they complete at least 70% of the planned contacts in the Tier 3 service, and take at least 70% of their planned doses of LIRA 3mg as stipulated by the prescribing pathway.

Participants that had Liraglutide 3mg outside of the treatment pathway (i.e. in the control group or in the intervention group after a stopping rule means they should have stopped taking Liraglutide 3mg) will be excluded from the per protocol population. The protocol deviations and in particular deviations from randomised treatment group in the protocol deviations will capture where this has occurred for any individual.

Participants who had bariatric surgery during the study period will be only be included at time-points prior to their bariatric surgery. They will be excluded from time-points after their bariatric surgery.

The binary variable of compliant with tier 3 service at 52 weeks will be used to exclude individuals that did not have 70% of planned visits for outcomes assessed at 52 weeks, likewise for outcomes assessed at 104 weeks the variable at 104 weeks will be used.

Individuals in the intervention arm that did not receive 70% of the doses as determined by the protocol (i.e. in the first 16 weeks or there after whilst continuing to meet the continue rules of the protocolised treatment schedule) will be excluded from the per protocol populations. The number of days taking LIRA and whether this corresponds to 70% of doses is defined in Appendix 7 in section 14. For outcomes at

the 52 week time point the definition in 14.1 should be used; while for outcomes at the 104 week time point the definition in 14.2 should be used.

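### A note in Protocol 8.3.2, read literally, continues LIRA once BMI falls below 35, whereas the stopping rules in 6.2 depend on percentage weight loss alone

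*Protocol*

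**What the plan says.** Protocol 6.2 sets three stopping rules, repeated in SAP 1.2.3.1. LIRA goes on only with a loss from baseline weight of at least 5% at week 16, 10% at week 32 and 15% at week 52. Of those who fall short, 6.2 says: "Participants who have not met this weight loss target will have their LIRA 3mg treatment stopped". Protocol 8.3.1.2, the week-16 and week-32 instructions in 8.4 and the week-52 bullets in 8.3.2 follow the same targets. None of them mentions BMI.

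The week-104 part of Protocol 8.3.2 contains a note on the maximum length of treatment, which ends: "For those participants that achieve more than 15% weight loss or a BMI" below 35 kg/m² "prior to the 104 weeks, treatment with LIRA 3mg will be continued unless the patient begins to experience side-effects". The two criteria are joined by *or*, so the BMI criterion is enough alone. Side-effects are the only exception named.

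SAP 3.3.3 removes from the per-protocol population anyone who took LIRA outside the pathway, including those "in the intervention group after a stopping rule means they should have stopped taking Liraglutide 3mg". It looks to recorded protocol deviations to find them. SAP Appendix 7 counts planned LIRA days up to the stopping point at which the participant failed the percentage rule.

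**The concern.** The stopping rules are what distinguishes the targeted pathway from simply adding LIRA to standard care. If one sentence of the protocol continues the drug where another stops it, two sites could treat the same participant differently and each point to the text.

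Three things are at stake:

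- **Exposure.** LIRA continued after a missed week-16 or week-32 target precedes the primary outcome. Continued after week 52, it bears on the 104-week outcomes.
- **Drug cost.** Protocol 6.4.2 costs LIRA on what was actually taken, so extra exposure enters the budget-impact result.
- **Per-protocol membership.** The SAP knows only the percentage rules. It has no category for a participant kept on LIRA by a site that relied on the 8.3.2 note.

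**Working it through.** The plan states no figure on this point, so there is none to reproduce. The check is whether a participant can satisfy the note and fail a stopping rule at the same visit.

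**Inputs**

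- Entry BMI (Protocol 7.2): "have a BMI ≥ 35 kg/m 2", with no upper limit.
- Targets (Protocol 6.2): L = 5%, 10% and 15% at weeks 16, 32 and 52.
- BMI criterion in the note (Protocol 8.3.2): below 35 kg/m², at any time before week 104. That period contains all three stopping points.
- Assumption: height is constant, so BMI falls in proportion to weight.

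**Formula.** A participant entering at BMI B reaches BMI 35 at a proportional loss of 1 − 35/B. The note and a rule with target L can disagree when 1 − 35/B < L, that is, when B < 35/(1 − L).

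| Stopping rule | L | Entry BMI below which conflict is possible | Example |
|---|---|---|---|
| Week 16 | 5% | 35/0.95 = 36.84 | entry 36.0, loss 3%: 36.0 × 0.97 = 34.92 |
| Week 32 | 10% | 35/0.90 = 38.89 | entry 38.0, loss 9%: 38.0 × 0.91 = 34.58 |
| Week 52 | 15% | 35/0.85 = 41.18 | entry 40.0, loss 13%: 40.0 × 0.87 = 34.80 |

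In each example 6.2 stops LIRA and the note, read literally, continues it.

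**Width of the conflict.** The loss must lie between 1 − 35/B and L:

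- Entry BMI 36 at week 16: 2.8% to 5%.
- Entry BMI 38 at week 32: 7.9% to 10%.
- Entry BMI 40 at week 52: 12.5% to 15%.
- Entry BMI 41 at week 52: 14.6% to 15%.
- Entry BMI 41.2: BMI 35 is reached only at 15.05%, so there is no conflict.

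All three rules can conflict with the note only for entry BMI below 36.8. The participant must also still be on LIRA. Under the percentage rules, the week-52 case therefore concerns only those who met 5% at week 16 and 10% at week 32.

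**The other criterion.** Someone above 15% loss before week 52 who is back below 15% at week 52 is continued by the note and stopped by the third rule, whatever the entry BMI.

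**Consequence in the SAP.** Take a participant who misses 5% at week 16 and is kept on LIRA to week 32. Appendix 7 plans 16 × 7 = 112 days, and 70% of that is 78.4 days. The participant has about 32 × 7 = 224 days and counts as having received the planned doses. Under 3.3.3 the same person is off the pathway. Exclusion then depends on whether a deviation was logged, and a site that believed it was following 8.3.2 might log none.

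**The case against.** The strongest reply is context. The note closes a week-104 bullet that opens with participants who are on LIRA, and it follows a statement of maximum duration. Under 6.2, anyone still on LIRA by then has passed all three targets. Eligibility, which includes BMI of at least 35, is re-checked at every visit (Protocol 8.3 and 8.4). A natural purpose of the note is therefore to say that success, or no longer meeting the entry BMI, is not a ground for stopping early. The visit-specific instructions are explicit: the week-52 bullet of 8.3.2 itself rules out further LIRA below 15%. To continue the drug in the week-16 example, a site would have to set aside 6.2 and 8.4 in favour of a week-104 bullet, and nothing in the documents shows that this happened.

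That reading is plausible and limits the point, but it does not remove it. The note neither states that meaning nor says that the stopping rules still apply, and its time reference covers weeks 16, 32 and 52.

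Two other parts of the reply stand:

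- **Side-effects.** A reader might infer that the side-effects exception clashes with Protocol 8.8.4, where "permanent discontinuation of LIRA 3mg should be a last resort", and with 8.8.5 on temporary stops. It does not. The note does not say whether such a stop is temporary or permanent, so it is compatible with both.
- **Timing.** The amendment history gives a study end date of 30/06/2022, and the SAP is a version 1.1 draft dated 01/08/2022. On those dates a protocol sentence can record what was meant but can hardly change treatment. The SAP part of the remedy keeps its full value.

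**Conclusion.** The point holds as a conflict between the literal note and the percentage-only rules in Protocol 6.2, 8.3.1.2, 8.4 and the week-52 bullet of 8.3.2. It is confined to participants still on LIRA who are below BMI 35 but short of the target, plus those who passed 15% and slipped back by week 52. For the BMI criterion, the entry-BMI limits are 36.8, 38.9 and 41.2 at weeks 16, 32 and 52, assuming constant height.

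Three stronger readings are tempting but not supported:

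- **That the note overrides all three rules for everyone entering at BMI 35 to 41.** The upper limit belongs to the week-52 rule alone, and the note may not have been meant as an override.
- **That the number affected can be derived from the share of the arm in this BMI band.** The documents give no BMI distribution, and being in the band is not the same as being in conflict. No count is given here.
- **That SAP 3.3.3 will remove these participants, or that the primary analysis set changes.** Removal is possible but not certain, because it runs through logged deviations. The primary analysis uses complete cases as randomised (SAP 4.1 and 5.4.1), so its population does not depend on the note.

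What can change is intervention-arm exposure, drug cost and per-protocol membership. This review takes no position on which clinical rule is right.

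**What to change.** **Protocol.** Reconcile the 8.3.2 note with 6.2 in one sentence. It should state whether the note changes the three stopping rules, or means only that no longer meeting the entry BMI is not a reason to stop. If the protocol can no longer be amended, record the sponsor's answer in a dated clarification and cite it in the SAP.

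**SAP, before it is finalised:**

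- Tie the exclusion for LIRA outside the pathway (3.3.3) and the planned-dose rows of Appendix 7 to that single rule.
- Identify these participants from recorded weights and LIRA dates, and not only from logged deviations.
- Flag and report by visit anyone kept on LIRA under the 8.3.2 wording after missing a target. This also supplies the count that cannot be estimated now.

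**Cost.** One protocol sentence, a few SAP lines and one derived flag. No new data are needed: weight, BMI and dispensing are in the Appendix 3 schedule, and Appendix 7 already derives LIRA dates.
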